6.2 Rationale

Hypothesis

We postulate that the aerosol inhaled route is practical and feasible and has an acceptable safety profile, in volunteers latently infected with *M.tb*. We hypothesise that the aerosol inhaled route of administration will induce greater mucosal immunity and comparable systemic immunity when compared to historical data of the IM (systemic) route of administration from previous studies in healthy volunteers.

Vaccine dosage

Trials of MVA85A to date have established 1×10^8 pfu as the optimal dose for intradermal injection in adults. Although the fractional delivered dose of aerosolised viral vectored vaccines to the mucosal surface may be considerably less than 25%, there is evidence that strong mucosal and systemic immune responses, comparable to the injectable route, are nevertheless achieved (16, 64).

As this trial will be the first time that aerosolised MVA85A is given to individuals with latent *M.tb* infection, we plan to begin with a low dose Starter Group, who will receive 1×10^7 pfu MVA85A by aerosol inhalation. This is the dose used in trial TB026 in healthy adults. The first volunteer in this group will be vaccinated ahead of other volunteers and no other volunteers will be vaccinated until at least 48 hours has elapsed. The CI will perform a review of the 48 hour safety data and decide if it is safe to vaccinate the remaining volunteers. There will be a second review of safety data after vaccination of all volunteers in the Starter Group.

Once the Starter Group is fully enrolled and the second safety review is completed, we will start enrolment into Group A (Standard Dose), with dose escalation to 5×10^7 pfu (the same dose used in TB035). For safety reasons, the first volunteer in this group will be vaccinated ahead of other volunteers and no other volunteers will be vaccinated until at least 48 hours has elapsed. If the CI

decides it is safe to proceed, the remaining volunteers will then be enrolled. The target enrolment for this group is 6 volunteers. However, given the often reduced pace of recruitment from the latently infected population, we will accept a minimum of 3 volunteers if the target has not been reached by October 2018.

6.3 Risks and Benefits

Potential risks

The potential risks to participants in this trial include risks associated with:

1. Venepuncture and intravenous cannulation

Localised bruising and discomfort can occur at the site of venepuncture. Infrequently fainting may occur. The total volume of blood drawn over a six month period will be 356mL, which should not compromise the health of these healthy individuals.

An intravenous cannula is routinely inserted into a peripheral (usually forearm) vein prior to bronchoscopy to administer intravenous sedation and removed once the procedure is completed. The risks of cannulation are identical to those associated with venepuncture. Additionally cannulation carries a small risk of soft tissue infection which will be minimised by an aseptic insertion technique and is easily recognisable and treatable. The short duration of cannulation (a few hours) further minimises this risk.

2. Vaccination

MVA85A has undergone thorough pre-clinical testing and has now been administered to over 2500 healthy human individuals with one possible SAR. The potential known adverse events associated with vaccination are:

Local reaction from aerosol inhaled vaccination

Expected reactions to inhaled vaccination include mild throat discomfort and coughing. Transient bronchospasm (causing wheeze) is possible. In the completed aerosolised trials (TB026 and TB035) there was no significant difference between respiratory adverse events or pulmonary function tests between the group receiving a priming immunisation with aerosol MVA85A and the group receiving a priming immunisation with ID MVA85A. In both groups AEs were infrequent and mild. In TB035, of the 9 subjects who received an aerosol boost vaccination 1 month after ID prime, 7 experienced transient mild to moderate respiratory AEs. All were self-limiting. This only occurred in subjects receiving an aerosol boost 1 month after an ID prime. The last 3 subjects in this group did not therefore receive an aerosol MVA85A boost.

Systemic reactions

Constitutional influenza-like symptoms such as fatigue, headache, malaise, feverishness, and muscle aches can occur with any vaccination and last for 2-3 days. In the case of MVA85A, fatigue and headache are most common, occurring in 50-90% of volunteers, and these are nearly always mild. Presyncopal and syncopal episodes may occur at the time of vaccination which rapidly resolve. As with any other vaccine, temporary ascending paralysis (the Guillain-Barré syndrome, GBS) or immune mediated reactions that can lead to organ damage may occur. For influenza vaccines an excess of approximately 1 GBS case per million persons immunised has been observed. No cases were observed in people under 45 years of age. However, this has never been seen with the MVA85A vaccine or vaccines containing any of its components.

TB specific risks

There is a very small risk of a Koch reaction, or immunopathology at the site of infection occurring when volunteers latently infected with *M.tb* are vaccinated with MVA85A. No such reactions were

seen in previous trial TB007, where MVA85A was administered systemically to volunteers with latent *M.tb* infection. All volunteers will be closely monitored and followed up both clinically and radiologically.

Allergic reactions

Allergic reactions from mild to severe may occur in response to any constituent of a vaccine preparation. Anaphylaxis is extremely rare but can occur in response to any vaccine.

3. Bronchoscopy

Bronchoscopy is a widely and safely used investigative procedure in clinical research studies involving both healthy volunteers and patients with respiratory conditions such as asthma and interstitial lung disease (60, 61). Clinical guidelines for performing investigative bronchoscopy in research studies are well established (62).

The bronchoscopies will be carried out in a dedicated NHS bronchoscopy suite with an excellent safety record by highly skilled and experienced consultant respiratory physicians. Intravenous sedation and topical local anaesthesia are administered prior to bronchoscopy to reduce discomfort, facilitate the procedure, and remove memory of the event (In 98% of cases, subjects have no memory of the procedure). Trained, experienced staff and facilities for resuscitation and drugs for reversal of sedation will be available. No transbronchial or endobronchial biopsies will be taken. To further minimise risk, volunteers will be excluded if they have an abnormal CT chest, a significant smoking history, a history of atopy, or any evidence of lung disease, including asthma (as defined by: a clinical diagnosis of asthma; prescription of asthma medication; airflow obstruction on spirometry; history of nocturnal or exercise-induced wheeze).

The risks of bronchoscopy are discussed at the time of consent and comprise: adverse reaction to sedation or local anaesthetic, sore throat, nose bleed (minimized as scope passed through mouth), laryngospasm, hypoxia, post-procedure flu-like symptoms (1-2 days) and risk of death (<1 in 100,000).

- Bronchoalveolar lavage is a routine procedure in investigative bronchoscopy and carries minimal bleeding risk. The risk of infection or febrile reactions will be minimised by full bronchoscope asepsis and superflush.
- Respiratory depression secondary to sedation is rare. No rescue medication for oversedation has been required for volunteers participating in trials TB026 and TB035 to date.
- Allergic reactions from mild to severe may occur in response to any constituent of the local anaesthetic or sedative agents. Anaphylaxis is extremely rare but can occur.

The Summary of Product Characteristics (SmPC) for the local anaesthetic and sedative agents contain full details of the indications and side effects of these licensed medications.

4. CT thorax

A computed tomography scan of the thorax is a painless radiological investigation which exposes volunteers to approximately 2 milliSieverts of radiation, equivalent to around 9 months of natural background radiation. The additional risk of cancer due to one CT thorax is small, approximately 1 in 9000. The total radiation exposure for this trial (two CT scans) will therefore be 4 milliSieverts, carrying an attributable cancer risk of 1 in 4500.

5. Pulmonary Function Tests

Vigorous respiratory manoeuvres such as forced expiration through the spirometer can occasionally lead to coughing or lightheadedness, but these symptoms are mild and rapidly self-limiting.

Potential benefits

Volunteers are not expected to benefit directly from participation in this trial. Volunteers will gain some information about their general health as a result of the screening history, examination, blood tests, urine tests, CT thorax and pulmonary function tests. They may also gain health information from the bronchoscopy. Volunteers found to have a previously undiagnosed condition thought to require further medical attention will be referred appropriately to their GP or an NHS specialist service for further investigation and treatment.

It is hoped that their contribution will enable the development of a safe and successful vaccine for TB and further our knowledge about mucosal vaccines.

7 OBJECTIVES AND OUTCOME MEASURES

Table 3. Objectives and Outcome Measures

Objectives	Outcome Measures	Timepoint(s) of evaluation of this outcome measure
Primary Objective To evaluate the safety of MVA85A vaccination by the aerosol inhaled route in healthy adult volunteers who are latently infected with M.tb .	Actively and passively collected data on adverse events	At each visit, via diary card for 14 days after vaccination and at the 6 month phone call
Secondary Objectives To evaluate the systemic and mucosal cellular and humoral immunogenicity induced by MVA85A vaccination by the aerosol inhaled route, in healthy volunteers who are latently infected with M.tb .	Laboratory markers of cell mediated and humoral immunity, including ex-vivo ELISpot in blood and intracellular cytokine staining in blood and BAL samples	At each visit
Tertiary Objectives To evaluate other exploratory markers of cell-mediated and humoral immunogenicity induced by aerosol MVA85A, including transcriptomic analysis	Laboratory markers of cell mediated and humoral immunity in blood and BAL samples	At each visit

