4.2 Schedule of visits and procedures

Table 1. Schedule of trial procedures

Attendance number	1	2	3	4	5	6	7	8
Timeline (days)*	S	0	2	7	14	28	84	168 ^T
Timeline (weeks)*	S	0		1	2	4	12	24
Time windows (days)			±1	+4, -2	±4	±7	±14	±21
Inclusion/exclusion criteria	X							
Review contra-indications	X	X		X				
Informed consent	X							
Medical history	X	(X)	(X)	(X)	(X)	(X)	(X)	(X)
Physical examination	X			X				
Vital signs	X	X	X	X	X	X	X	
Urinalysis	X							
CT chest	X					X		
PFTs	X	X	X	X	X			
β-HCG urine test	X	X		X				
Vaccinations		X						
Bronchoscopy				X				
Local & systemic events/reactions		X	X	X	X	X	X	X
Ediary setup		X						
Ediary final review					X			
Biochemistry (4mL)**	X		X	X		X		
Haematology (2mL)	X			X		X		
Coagulation (4mL)	X							
HBV, HCV, HIV (10mL)	X							
HLA typing (4mL)		X						
Exploratory immunology incl ELISpot (16-60mL***)	X	X	X	X	X	X	X	
Blood vol (mL)	30	64	20	56	60	66	60	
Cumulative blood vol (mL)****	30	94	114	170	230	296	356	

S Screening

X Event scheduled to occur

(X) If considered necessary, emphasising any complaint or change in medications

T Telephone call. Final visit is deemed to be at D84 with follow up phone call at D168

* Timeline is approximate only, as exact timings (± windows periods) of visits relate to the actual (not intended) date of the previous visit

** U&Es, LFTs (except day 2 when CRP only;)

*** 60ml at all visits except screening (10ml, T spot), visit 3 (16ml, no ELISpot) and visit 4 (50ml)

**** Blood volumes stated for Oxford. The exact volumes of blood taken will depend on the local site – cumulative blood volumes for volunteers outside Oxford may be slightly lower or higher than those of Oxford volunteers, due to the use of different volume vacutainers for biochemistry, haematology and serology samples as per local Trust standard procedures

Grey Highlights vaccination day

Blue Highlights bronchoscopy day

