Aerosol delivery of a candidate TB vaccine, therefore, shows promise; however, before this potential route of vaccine administration can be evaluated in TB high burden countries, it is imperative that safety in subjects with latent *M.tb* infection be determined, because of the theoretical risk of immunopathology. This trial aims to assess safety and immunogenicity of aerosol MVA85A vaccination by repeating our previous phase I clinical trial of aerosol MVA85A vaccination in healthy adults (35) in UK adult human volunteers with latent *M.tb* infection. The essential safety and immunogenicity data that will be generated from this trial is a critical go/no-go criteria before this potentially promising route of vaccination can be evaluated in TB high burden countries, where an improved TB vaccine is most needed.

Description and pre-clinical experience of MVA and MVA85A

Modified vaccinia virus Ankara (MVA) is a highly attenuated strain of vaccinia virus which cannot replicate in human cells. It is known to be highly immunogenic and is therefore suitable for use as a viral vector in new vaccine development. It has an excellent safety record as it was administered intradermally to approximately 120,000 people during the smallpox eradication campaign (36-39), and

has since been used in numerous clinical trials of candidate vaccines against viral, mycobacterial and protozoal infections (40, 41). Meanwhile recombinant MVA vaccines administered by respiratory mucosal and gut mucosal routes have demonstrated protective efficacy and elicited strong immune responses in both rodents and non-human primates (42).

Antigen 85A is a highly conserved antigen expressed by *M.tb*, BCG, and all other mycobacterial species sequenced to date. It is a 32-kDa protein, and is an enzyme, mycolyl transferase, which is involved in cell wall biosynthesis (43). Antigen 85A is highly immunodominant in both animal and human studies (44-46), and protects against *M.tb* challenge in mice, guinea pigs and non-human primates (47, 48). The recombinant MVA85A vaccine incorporates the 1176 base pair gene for antigen 85A into the viral DNA allowing expression of this secreted antigen.

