9.6 Timepoints

Screening – trial enrolment time window

Enrolment should take place no longer than 120 days following the date of screening appointment. If more than 120 days elapse, the screening visit should be repeated in full prior to enrolment in order to minimise the risk to participants of any new unidentified health problems having arisen during that period.

Vaccination of first volunteer – subsequent vaccination time window

The first volunteer, who will be allocated to the Starter Group, will be vaccinated with MVA85A by the aerosol inhaled route at least 48 hours before any subsequent volunteers in this group. After safety review, the first volunteer in Group A will be vaccinated at least 48 hours prior to further enrolment.

Vaccination – bronchoscopy time window

According to our clinical research (and in line with pre-clinical findings), the peak effector T cell response detected from PBMC in venous blood samples is around seven days after vaccination with MVA85A. In our previous trial of aerosolised MVA85A, high frequencies of Ag85A-specific cytokines were detected in BAL samples at one week post-vaccination, therefore bronchoscopy will be performed at seven days to match that trial.

Follow up period

The follow up period will be six months in accordance with findings from previous trials in which adequate safety data and reliable markers of immunogenicity have been obtained in this time interval.

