11.6 Reporting Procedures for All Adverse Events

All AEs occurring in the 14 days following each vaccination observed by the Investigator or reported by the volunteer, whether or not attributed to study medication, will be recorded on electronic diary cards. Data from the diary cards will be extracted at each safety review and following the last volunteer last visit (LVLV). Outside the diary card periods, expected local and systemic AEs (listed in table 7 below) will be specifically solicited at each visit, and graded by severity and causality (as detailed in sections 11.7 and 11.5). All AEs starting after the diary card period, or persisting after this period, will be recorded in the AE line listing of the CRF.

The overall appearance of the lung mucosa will be assessed at the day 7 bronchoscopy.

Any radiological changes to the lungs will be assessed at the day 28 CT thorax.

All AEs that result in a volunteer's withdrawal from the study will be followed up until a satisfactory resolution occurs, or until a non-study related causality is assigned (if the volunteer consents to this). Serious adverse events (SAEs) will be collected throughout the entire trial period.

Reporting Procedures for Serious AEs (see Safety Reporting SOP)

In order to comply with current regulations on serious adverse event reporting to regulatory authorities, the event will be documented accurately and notification deadlines respected. SAEs will be reported on the SAE forms to members of the study team immediately the Investigators become aware of their occurrence, as described in the site-specific SOP. Copies of all reports will be forwarded for review to the Chief Investigator and Principal Investigators (as the Sponsor's representatives) within 24 hours of the Investigator being aware of the suspected SAE. The local safety committee (LSC) will be notified of SAEs which are deemed possibly, probably or definitely related to study interventions; the LSC will be notified immediately (within 24 hours) of the Investigators' being aware of their occurrence. SAEs will not normally be reported immediately to the ethical committee(s) unless there is a clinically important increase in occurrence rate, an unexpected outcome, or a new event

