12 STATISTICS

This is primarily a safety trial with descriptive endpoints. Following the first three volunteers enrolled into the starter group, 3-6 volunteers will be recruited into Group A, to receive the target dose. Due to existing difficulties recruiting to this clinical trial we have decided to take out Group B (the comparator arm) to ensure that the numbers recruited will still be sufficient to allow for the primary objective, an assessment of safety. A twofold increase in the magnitude of the cellular immune response (as measured by ELISpot response to 85A peptide stimulation) is considered immunologically

meaningful. This sample size is appropriate for a proof-of-concept Phase I safety study and takes into account the low number of potentially eligible healthy adults with latent *M.tb* infection in the UK and the impact of this on recruitment. The sample size has not been determined with the aim of achieving statistical significance.

It is anticipated that the immunological endpoints will not follow a normal distribution. The one-week and three-month responses will be compared. Medians and interquartile ranges will be used to summarise the data and the Mann Whitney U test will be used for statistical comparisons. An area-under-curve analysis will be used to compare the overall responses over time comparing these aerosol data with historical data from previous trials. This analysis will make use of data collected at all time points.

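### One BAL sample at day 7, with no baseline and no concurrent control, can describe mucosal responses but cannot show that vaccination induced them or that they exceed the IM route

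*Combined protocol and SAP*

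**What the plan says.** The secondary objective in section 7 (Table 3) is "To evaluate the systemic and mucosal cellular and humoral immunogenicity induced by MVA85A vaccination by the aerosol inhaled route", in latently infected volunteers. The mucosal part is measured by "intracellular cytokine staining in blood and BAL samples", and Table 3 gives the time point as every visit. Section 6.2 hypothesises that the aerosol route "will induce greater mucosal immunity and comparable systemic immunity when compared to" historical intramuscular (IM) data from healthy volunteers.

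Table 1 (section 4.2) marks bronchoscopy once, in the day 7 column. Section 9.6 explains the timing by reference to the previous aerosol trial: "therefore bronchoscopy will be performed at seven days to match that trial". Blood is different. The Table 1 footnote on immunology volumes reads "60ml at all visits except screening (10ml, T spot), visit 3 (16ml, no ELISpot) and visit 4 (50ml"; day 0 is not among the exceptions, so a full pre-vaccination blood sample is taken.

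Section 12 says "we have decided to take out Group B (the comparator arm"). Table 4 (section 9.1) leaves two groups, both given aerosol MVA85A. Section 12 then plans to compare one-week with three-month responses and to compare areas under the curve with historical data.

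Section 8.2 requires a positive screening IGRA. Section 6.1 says that "Antigen 85A is highly immunodominant in both animal and human studies" and that M.tb, BCG and every other sequenced mycobacterial species express it.

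**The concern.** Induced is a causal word and greater is a comparative one. To support the first, BAL needs a pre-vaccination value or comparable unvaccinated people. To support the second, it needs a comparator that differs in route and in little else. The plan gives BAL neither.

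The population makes this more than a formality. The volunteers carry an infection whose organism expresses the vaccine antigen. Section 6.1 places primary infection in the lung, and section 8.2 admits volunteers whose CT shows signs of primary infection. Some 85A-specific response in BAL before vaccination is therefore plausible.

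What is at stake is how a BAL result would be read. Section 6.1 treats the trial's safety and immunogenicity data as decisive for taking the route into high-burden countries. A day 7 BAL level that partly reflects infection could be reported as a vaccine effect, and the plan contains nothing to prevent that reading.

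**Working it through.** The plan gives no power, alpha or standard deviation to reproduce. The check is a count of samples and comparators, followed by what each planned contrast estimates.

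**Inputs**
- BAL before vaccination: 0 per person (Table 1, screening and day 0 columns).
- BAL after vaccination: 1 per person, at day 7 (Table 1; sections 9.5 and 9.6).
- Volunteers: Starter Group 3 and Group A 3 to 6, so 3 + 3 = 6 to 3 + 6 = 9 (Table 4). Unvaccinated: 0.
- Human BAL results described: TB026 only, aerosol against intradermal, in BCG-vaccinated healthy adults (section 6.1, Table 2). Section 6.3 implies that TB035 also included bronchoscopy, but the protocol reports no BAL results from it. No IM BAL results are described.

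**Step 1: within-person change.** Write the day 7 BAL response as Y = B + V, with B the pre-existing and V the induced part. One value is observed and two are unknown. Without a pre-vaccination sample, or an estimate of B from comparable unvaccinated people, V is not estimable.

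**Step 2: the section 12 analyses.** The one-week against three-month comparison needs a three-month BAL, and there is none. An area under the curve needs at least two time points, and BAL has one. Neither analysis applies to BAL, and Table 3's every-visit time point cannot apply either.

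**Step 3: the historical contrast.** Let L be this cohort and H the historical one. The expected difference in day 7 BAL is

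(B_L − B_H) + (V_L − V_H).

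The hypothesis concerns the second bracket; the data give only the sum. Infection status is L for everyone here and H for everyone there, so it cannot be separated from route.

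**Step 4: the dose contrast.** This is the only comparison inside the trial. The smallest exact two-sided Mann-Whitney p-value is 2/C(n1+n2, n1):
- 3 v 3: 2/20 = 0.10
- 3 v 4: 2/35 = 0.057
- 3 v 5: 2/56 = 0.036
- 3 v 6: 2/84 = 0.024

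Both groups are vaccinated, so a dose trend would be weak, indirect evidence of induction.

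**Step 5: illustration only.** Suppose day 7 BAL levels differ by a fixed ratio because of infection status alone, with nothing else differing between cohorts. Assume 12 historical samples, log10-normal data and an exact two-sided Mann-Whitney test at 0.05. The share of 4,000 simulated trials declared significant is:

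| Assumed ratio | log10 SD | n = 3 | n = 6 | n = 9 |
|---|---|---|---|---|
| 1 (no difference) | 0.3 | 4% | 4% | 5% |
| 1.5 | 0.3 | 14% | 16% | 23% |
| 2 | 0.3 | 28% | 41% | 55% |
| 3 | 0.3 | 59% | 79% | 91% |
| 1 (no difference) | 0.5 | 5% | 4% | 5% |
| 1.5 | 0.5 | 8% | 9% | 11% |
| 2 | 0.5 | 13% | 17% | 24% |
| 3 | 0.5 | 27% | 37% | 51% |

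By symmetry, the inverse ratios give the same rates in the opposite direction. The ratios, SDs and number of historical samples are all assumed. The table shows that a test against historical BAL data could mislead; it does not estimate how far this trial would be misled.

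**The case against.** The strongest reply has four parts.

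- **Historical data exist.** TB026 has BAL after aerosol and intradermal MVA85A, its main aerosol dose equals the Starter Group dose, and bronchoscopy here is timed to match it. That gives useful context. But TB026 as described has no unvaccinated BAL, no latently infected cohort and no IM arm, so it cannot separate B from V or answer the hypothesis as stated.
- **The trial is descriptive.** Section 12 frames it as a safety study not sized for significance, and no BAL test or mucosal success criterion is set. This limits the consequence. It is also a reason to word the mucosal objective descriptively.
- **Bronchoscopy is invasive and sedated.** One BAL per volunteer is a defensible choice, and nothing here asks for another.
- **A caveat might do.** Ruling out a superiority conclusion could be called excessive. The historical comparison can stay as exploratory, but a caveat beside a hypothesis that still says greater would leave the claim standing.

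A reader might infer more than the documents support:

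- **That there is no comparator of any kind.** The plan names historical data; what is missing is a concurrent or unvaccinated control.
- **That latently infected lungs are known to hold 85A responses, so bias must favour the hypothesis.** The documents give no pre-vaccination BAL figure, and IGRA positivity is not described as a measure of 85A. TB026 volunteers were BCG-vaccinated, and BCG expresses 85A, so they too had prior exposure.
- **That removing Group B created the gap.** The amendment history (section 2) shows that Group B was to receive IM MVA85A. It would have helped the route contrast, but it was vaccinated too and would not by itself have separated pre-existing from induced response.

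**Conclusion.** The point holds for the mucosal part of the secondary objective and of the hypothesis. With no BAL before vaccination, one after it and no concurrent control, induction in the lung is not estimable. Superiority over historical IM data is confounded with infection status and has no described IM BAL data behind it.

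Non-identifiability follows from the visit schedule and needs no assumption about B. That B is above zero is an inference from sections 6.1 and 8.2. The size and direction of any resulting bias are unknown.

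The primary safety objective is untouched. The systemic part has a day 0 sample, so change in blood can be estimated. Calling that change induced still assumes that nothing other than vaccination shifted the response. The consequence is an overstated secondary claim that should be corrected before BAL results are interpreted.

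**What to change.** No procedure is added.

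1. In section 7 (Table 3), the synopsis and section 6.2, reword the mucosal part as a description of 85A-specific responses in BAL at day 7 after vaccination. In Table 3, give BAL its own time point in place of every visit.
2. In section 12, state that BAL data will be summarised descriptively. State also that any comparison with historical BAL data is exploratory and confounded by population, prior exposure and lack of a baseline, and that it will not support a conclusion of mucosal induction or superiority.
3. Keep the word induced for blood, and analyse blood responses as within-person change from the day 0 sample already collected. If a signed-rank test is used, its smallest two-sided p-value is 2/2^n: 0.25 with n = 3, 0.031 with n = 6 and 0.0039 with n = 9. A dose group of 3 can therefore only be described.

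The cost is a change of wording and a weaker mucosal claim.
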